Appendix 4 Clinical Laboratory Tests

The tests detailed in [Table 1](#) will be performed locally for Part 1 of the study and by the central laboratory for Part 2 (with the exception of urinalysis specific gravity, urine dipstick, and alcohol testing which will be performed locally).

In Part 2, local laboratory results are only required in the event that the central laboratory results are not available in time for either study treatment administration and/or response evaluation. If a local sample is required, it is important that the sample for central analysis is obtained at the same time. Additionally, if the local laboratory results are used to make either a study treatment decision or response evaluation, the results must be captured in source documentation and entered as a comment into the eCRF.

Protocol-specific requirements for inclusion or exclusion of participants are detailed in Sections [5.1](#) and [5.2](#), respectively, of the protocol.

Additional tests may be performed at any time during the study as determined necessary by the Investigator or required by local regulations.

Table 1 Protocol-Required Safety Laboratory Assessments

Laboratory Assessments	Parameters
Hematology	
 Leucocytes, erythrocytes, hemoglobin, hematocrit, platelets, differential count (neutrophils, eosinophils, basophils, monocytes, lymphocytes, other cells).
Clinical Chemistry	
 Sodium, potassium, chloride, bicarbonate, glucose, urea, creatinine, cystatin C (and estimated creatinine- and cystatin C-based eGFR by CKD-epi equation [see Appendix 6]) total protein, albumin, phosphate, calcium, total and direct bilirubin, gamma-glutamyl transferase (GGT), alkaline phosphatase, ALT, AST, urate. In Part 2, Creatinine Kinase (CK) will be performed as reflex testing on any AST value $\geq 2 \times$ ULN. 
For additional assessments relating to exploratory safety BMs, please see Section 8.6.1.

Coagulation	
 INR, aPTT/ PT.
Viral Serology (Part 1)	
 HIV (HIV-1 antibody, HIV-1/2 antibody, HIV-2 antibody), Hepatitis B surface antigen (HBsAg), total hepatitis B core antibody (anti-HBc), hepatitis C virus (HCV) antibody.
Viral Serology (Part 2)	
 HIV (HIV-1 antibody, HIV-1/2 antibody, HIV-2 antibody), hepatitis C virus (HCV) antibody.
Pregnancy Test	
 All women will have a blood pregnancy test at screening. Urine pregnancy tests will be performed at specified subsequent visits. If a urine pregnancy test is positive, it must be confirmed by a blood pregnancy test.
Urinalysis	
 Specific gravity 
Dipstick: pH, glucose, protein, blood, ketones leukocytes, nitrites.
 
If there is a clinically significant positive result (confirmed by a positive repeated sample), urine will be sent to the laboratory for microscopy and culture. If there is an explanation for the positive dipstick results (e.g., menses), it should be recorded and there is no need to perform microscopy and culture.
 
 Microscopic examination (sediment, RBCs, WBCs, casts, crystals, epithelial cells, bacteria), if there is a clinically significant positive result.
Other Screening Tests	
 Alcohol and drug screen as per local procedure (to include at minimum: amphetamines, barbiturates, cocaine, opiates, cannabinoids and benzodiazepines).

Investigators must document their review of each laboratory safety report.

Laboratory/analyte results that could unblind the study, will not be reported to investigative sites or other blinded personnel until the study has been unblinded.

Additional Statistical Considerations for Clinical Laboratory Data

- **Standard Reference Ranges and Transformation of Data**

Roche standard reference ranges, rather than the reference ranges of the Investigator, will be used for all parameters. For most parameters, the measured laboratory test result will be assessed directly using the Roche standard reference range. Certain laboratory parameters will be transformed to Roche's standard reference ranges.

A transformation will be performed on certain laboratory tests that lack sufficiently common procedures and have a wide range of Investigator ranges, e.g., enzyme tests that include AST, ALT, and alkaline phosphatase and total bilirubin. Since the standard reference ranges for these parameters have a lower limit of zero, only the upper limits of the ranges will be used in transforming the data.

- **Definition of Laboratory Abnormalities**

For all laboratory parameters included, there exists a Roche predefined standard reference range. Laboratory values falling outside this standard reference range will be labeled "H" for high or "L" for low in participant listings of laboratory data.

In addition to the standard reference range, a marked reference range has been predefined by Roche for each laboratory parameter. The marked reference range is broader than the standard reference range. Values falling outside the marked reference range that also represent a defined change from baseline will be considered marked laboratory abnormalities (i.e., potentially clinically relevant). If a baseline value is not available for a participant, the midpoint of the standard reference range will be used as the participant's baseline value for the purposes of determining marked laboratory abnormalities. Marked laboratory abnormalities will be labeled in the participant listings as "HH" for very high or "LL" for very low.

Appendix 5 Contraceptive Guidance and Collection of Pregnancy Information

1. DEFINITIONS

- **Woman of Childbearing Potential (WOCBP)**

A woman is considered fertile following menarche and until becoming post-menopausal unless permanently sterile.

- **Women in the following categories are considered to be Woman of Non-Childbearing Potential (WONCBP)**

- a) Pre-menarchal

- b) Pre-menopausal female with one of the following:

- Documented hysterectomy.
- Documented bilateral salpingectomy.
- Documented bilateral oophorectomy.

Note: Documentation can come from the site personnel's: review of participant's medical records, medical examination, or medical history interview.

- c) Post-menopausal female

- A post-menopausal state is defined as no menses for ≥ 12 months without an alternative medical cause other than menopause.
- Females on HRT and whose menopausal status is in doubt will be required to use one of the non-hormonal highly effective contraception methods if they wish to continue their HRT during the study. Otherwise, they must discontinue HRT to allow confirmation of post-menopausal status before study enrollment.

2. CONTRACEPTION GUIDANCE

• Female Participants

Only female participants of non-childbearing potential are eligible to participate. Per ICH M3(R2), highly effective methods of birth control are defined as those, alone or in combination, that result in a low failure rate (i.e. less than 1% per year) when used consistently and correctly as described in [Table 1](#) below.

Table 1 Highly Effective Contraceptive Methods

Highly Effective Contraceptive Methods That Are User-Dependent^a (Failure rate of < 1% per year when used consistently and correctly)
Combined (estrogen- and progestogen-containing) hormonal contraception associated with inhibition of ovulation 
• Oral• Intravaginal• Transdermal Progestogen-only hormonal contraception associated with inhibition of ovulation 
• Oral• Injectable
Highly Effective Methods That Are User-Independent^a
Implantable progestogen-only hormonal contraception associated with inhibition of ovulation 
• Intrauterine device (IUD)• Intrauterine hormone-releasing system (IUS)• Bilateral tubal occlusion Vasectomized partner 
A vasectomized partner is a highly effective contraception method provided that the partner is the sole male sexual partner of the WOCBP and the absence of sperm has been confirmed. If not, an additional highly effective method of contraception should be used.
 Sexual abstinence 
Sexual abstinence is considered a highly effective method only if defined as refraining from heterosexual intercourse during the entire period of risk associated with the study treatment. The reliability of sexual abstinence needs to be evaluated in relation to the duration of the study and the preferred and usual lifestyle of the participant.

a) Typical use failure rates may differ from those when used consistently and correctly. Use should be consistent with local regulations regarding the use of contraceptive methods for participants participating in clinical studies.

3. PREGNANCY TESTING

For WOCBP enrolled in the study, blood sample and urine pregnancy tests will be performed according to SoA tables (see Section 1.3). If a urine pregnancy test is positive, it must be confirmed by a blood pregnancy test.

Pregnancy testing will be performed whenever a menstrual cycle is missed or when pregnancy is otherwise suspected and according to local practice.

4. COLLECTION OF PREGNANCY INFORMATION

- **Male participants with partners who become pregnant**

The Investigator will attempt to collect pregnancy information on any male participant's female partner who becomes pregnant while the male participant is in this study (see Section 8.3.5 Pregnancy). This applies only to male participants who receive RO7239958.

Attempts should be made to collect and report details of the course and outcome of any pregnancy in the partner of a male participant exposed to study treatment. The Investigator will record pregnancy information on the Clinical Trial Pregnancy Reporting Form and submit it to the Sponsor within 24 hours of learning of the partner's pregnancy. When permitted by the site, the pregnant partner would need to sign an Authorization for Use and Disclosure of Pregnancy Health Information to allow for follow-up on her pregnancy. If the authorization has been signed, the Investigator should update the Clinical Trial Pregnancy Reporting Form with additional information on the course and outcome of the pregnancy when available. An Investigator who is contacted by the male participant or his pregnant partner may provide information on the risks of the pregnancy and the possible effects on the fetus, to support an informed decision in cooperation with the treating physician and/or obstetrician. The female partner will be followed to determine the outcome of the pregnancy. Information on the status of the mother and child will be forwarded to the Sponsor. Monitoring of the participant's partner should continue until conclusion of the pregnancy. Any termination of the pregnancy will be reported regardless of fetal status (presence or absence of anomalies) or indication for procedure.

- **Female participants who become pregnant**

The Investigator will collect pregnancy information on any female participant, who becomes pregnant while participating in this study (see Section 8.3.5 Pregnancy). Information will be recorded on the appropriate form and submitted to the Sponsor within 24 hours of learning of a participant's pregnancy. The participant will be followed to determine the outcome of the pregnancy. The Investigator will collect follow-up information on the participant and the neonate, which will be forwarded to the Sponsor. Monitoring of the participant should continue until conclusion of the pregnancy. Any termination of pregnancy will be reported, regardless of fetal status (presence or absence of anomalies) or indication for procedure.

While pregnancy itself is not considered to be an AE or SAE, and should not be recorded on the AE eCRF, any pregnancy complication will be reported as an AE or SAE. A spontaneous abortion is always considered to be an SAE and will be reported as such. Any post-study pregnancy related SAE considered reasonably related to the study treatment by the Investigator, will be reported to the Sponsor as described in [Appendix 2](#). While the Investigator is not obligated to actively seek this information in former study participants, he/she may learn of an SAE through spontaneous reporting.

Any female participant who becomes pregnant while participating in the study will discontinue study treatment.

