6. TREATMENTS

Study treatment is defined as any investigational treatment(s), marketed product(s), placebo, or medical device(s) intended to be administered to a study participant according to the study protocol.

The investigational medicinal products (IMP) required for completion of this study are RO7239958 and placebo. RO7239958 will be provided by the Sponsor. Placebo will be provided by the site. All RO7239958 doses and placebo will be administered by investigational staff (i.e., the Investigator or study nurse) at the study clinic in the morning and in the fasted state (either two hours before or two hours after a meal). After SC administration of study drug, Part 2 participants should remain at the site at least until the post-dose assessments are completed.

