8.3.5 Pregnancy

Male participants will be instructed through the Informed Consent Form (ICF) to immediately inform the Investigator if their partner becomes pregnant during the study or within 105 days after the last dose of study drug.

If a pregnancy is reported, the Investigator should inform the Sponsor within 24 hours of learning of the pregnancy and should follow the pregnancy reporting process as detailed in [Appendix 5](#).

Abnormal pregnancy outcomes (e.g., spontaneous abortion, fetal death, stillbirth, congenital anomalies, ectopic pregnancy) are considered SAEs ([Appendix 5](#)).

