9.3 POPULATIONS FOR ANALYSES

For the purpose of analysis, the following populations are defined in [Table 11](#).

Table 11 Analysis Populations

Population	Description
Safety	All study subjects who have received at least one dose of the study medication, whether prematurely withdrawn from the study or not, will be included in the safety analysis.
Pharmacokinetic	Study subjects will be excluded from the PK analysis population if they significantly violate the inclusion or exclusion criteria or deviate significantly from the protocol, or if data are unavailable or insufficiently complete to allow the analysis. Excluded cases will be documented together with the reason for exclusion. All decisions on exclusions from the analysis will be made prior to database closure.
Efficacy	The analyses of viral dynamic response in Part 2a (and potentially Part 2b) of the study will include all patients who were randomized and received at least one dose of study drug (RO7239958 or placebo) and with at least one post-treatment assessment. Participants will be analyzed according to the treatment group to which they are randomized.

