5. IMMEDIATE REPORTING REQUIREMENTS FROM INVESTIGATOR TO SPONSOR

Certain events require immediate reporting to allow the Sponsor to take appropriate measures to address potential new risks in a clinical trial. The Investigator must report such events to the Sponsor immediately; under no circumstances should reporting take place more than 24 hours after the Investigator learns of the event. The following is a list of events that the Investigator must report to the Sponsor within 24 hours after learning of the event, regardless of relationship to study treatment:

- Serious adverse events
- Non-serious adverse events of special interest (NSAESI)
- Pregnancies (see Section [8.3.5](#))

The Investigator must report new significant follow-up information for these events to the Sponsor immediately (i.e., no more than 24 hours after becoming aware of the information). New significant information includes the following:

- New signs or symptoms or a change in the diagnosis.
- Significant new diagnostic test results.
- Change in causality based on new information.
- Change in the event's outcome, including recovery.
- Additional narrative information on the clinical course of the event.

Investigators must also comply with local requirements for reporting serious adverse events to the local Health Authority and IRB/EC.

5.1 REPORTING REQUIREMENTS OF SERIOUS ADVERSE EVENTS AND NON-SERIOUS ADVERSE EVENTS OF SPECIAL INTEREST

Events that Occur prior to Study Treatment Initiation

After informed consent has been obtained but prior to initiation of study treatment, only serious adverse events caused by a protocol-mandated intervention should be reported. The Serious Adverse Event/Adverse Event of Special Interest Reporting Form provided to Investigators should be completed and submitted to the Serious Adverse Event Responsible immediately (i.e., no more than 24 hours after learning of the event).

Events that Occur after Study Treatment Initiation

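### Appendix 5 limits partner-pregnancy collection to men who receive RO7239958, which conflicts with the rest of the protocol and cannot be applied under the blind

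*Combined protocol and SAP*

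**What the plan says.** Appendix 5 Section 4 asks the Investigator to collect information when a male participant's partner becomes pregnant, and then restricts this: "This applies only to male participants who receive RO7239958".

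Other parts of the protocol are wider:

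- **Appendix 5 Section 4, next paragraph:** course and outcome are to be sought for "any pregnancy in the partner of a male participant exposed to study treatment".
- **Section 6:** "Study treatment is defined as any investigational treatment(s), marketed product(s), placebo, or medical device(s) intended to be administered to a study participant". Placebo is therefore study treatment.
- **Section 8.3.5:** male participants are told to "immediately inform the Investigator if their partner becomes pregnant during the study or within 105 days after the last dose of study drug". The Investigator informs the Sponsor within 24 hours and follows the process in Appendix 5. The section adds: "Abnormal pregnancy outcomes (e.g., spontaneous abortion, fetal death, stillbirth, congenital anomalies, ectopic pregnancy) are considered SAEs".
- **Section 8.3.3.1:** every pregnancy reported during the study is followed to its outcome.
- **Appendix 2 Section 5:** pregnancies are among the events the Investigator "must report to the Sponsor within 24 hours after learning of the event, regardless of relationship to study treatment".
- **Appendix 5 Section 6:** a congenital anomaly in a child of a male patient's partner is an SAE if he was exposed to study treatment.

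Section 6.3.2 blinds the participant, the Investigator and all site staff in direct contact with the participant, except the pharmacist. The primary objective (Section 3, Table 7) is safety and tolerability compared with placebo.

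**The concern.** The sentence is an operative instruction, and it sits in the appendix to which Section 8.3.5 sends the site for the pregnancy process. A site that reads only Appendix 5 may conclude that placebo recipients are outside the procedure. A site that reads the body of the protocol will conclude the opposite.

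Two things are at stake. First, the rule depends on treatment assignment but is given to someone who is blinded, so following it literally creates a reason to break the code. Second, abnormal pregnancy outcomes are SAEs. If they were collected on active and not on placebo, the two groups would be observed differently for one class of event, under an objective that compares them. Female participants must be of non-childbearing potential (Section 5.1), so partner pregnancy is the main route by which such events could arise.

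**Working it through.** **1. The scope in each place.**

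- Appendix 5 Section 4, restricting sentence: active only.
- Appendix 5 Section 4, next paragraph, read with Section 6: active and placebo.
- Appendix 5 Section 6, read with Section 6: active and placebo.
- Section 8.3.5: all male participants. The 105-day window runs from study drug, a term that Section 9.3 spells out as covering either product.
- Section 8.3.3.1: all reported pregnancies.
- Appendix 2 Section 5: pregnancies, with no limit by arm. The words there about relationship to treatment concern causality, so the relevant point is only that the pregnancy entry carries no arm restriction.

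One sentence is narrow and five places are not. The narrow sentence is unlikely to be shorthand for both products, because the male contraception rule in Section 5.1 names RO7239958 or placebo where it means both.

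**2. Can the narrow rule be carried out?** The Investigator collects the information and is blinded. For Part 2, Section 6.3.2 reserves code-breaking for emergencies in the patient's medical management. For any other reason the Medical Monitor should be contacted first, if possible. Deciding whether to fill in a pregnancy form is not such an emergency. During the blinded period the sentence must either be ignored or prompt an unblinding. It could take effect later: Appendix 5 continues monitoring until the pregnancy ends, whereas scheduled follow-up stops 84 days after the last dose (Section 4.1.1). A pregnancy can therefore outlast the blind. This is an inference from the timelines, not a stated plan.

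**3. Size of the placebo group (Section 9.2).** The plan's own totals reproduce:

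- Part 1: 4 × 10 = 40 to 5 × 10 = 50
- Part 2: 4 × 7 = 28 to 7 × 7 = 49

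Placebo:

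- Part 1: 4 × 2 = 8 to 5 × 2 = 10
- Part 2: 4 × 1 = 4 to 7 × 1 = 7
- Total: 12 of 68 (17.6%) to 17 of 99 (17.2%)

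Active:

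- Part 1: 32 to 40
- Part 2: 24 to 42
- Total: 56 to 82

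Replacements (Sections 7.1 and 7.2) and over-enrolment of up to two per arm in Part 2 (Section 5.5) are not counted.

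**4. Expected placebo partner pregnancies (illustration).** The documents give no pregnancy rate. Assumptions:

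- Every placebo participant is a man with a partner of childbearing potential, which overstates the number at risk.
- The partner pregnancy rate is 0.1% to 1% per year. The upper end is the contraceptive failure ceiling in Section 5.1; the lower end is assumed.
- The window runs from first dose to 105 days after last dose: 105 days in Part 1, 28 + 105 = 133 in Part 2a, 84 + 105 = 189 in Part 2b.

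Person-time on placebo:

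- Smallest design: 8 × 105 + 4 × 133 = 1,372 days, or 1,372 / 365.25 = 3.76 years
- Largest design: 10 × 105 + 5 × 133 + 2 × 189 = 2,093 days, or 2,093 / 365.25 = 5.73 years

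Expected pregnancies m = years × rate:

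- Lowest: 3.76 × 0.001 = 0.0038
- Highest: 5.73 × 0.01 = 0.057

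The chance of at least one, 1 − exp(−m), runs from about 0.4% to 5.6%. To expect one placebo partner pregnancy even in the largest design, the rate would have to be 1 / 5.73, about 17% per year. Abnormal outcomes would be fewer than pregnancies.

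**The case against.** The strongest reply is that nothing is lost in practice. Sections 8.3.3.1 and 8.3.5 and Appendix 2 Section 5 already require reporting and follow-up in both arms. A blinded Investigator has no means of leaving out placebo partners, so the workable course is to collect for everyone. The study has no hypothesis tests, safety is summarised descriptively, and the safety population consists of dosed participants, not their partners.

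Most of this stands, and it limits the point. A reader might infer from the restricting sentence that all placebo partner pregnancies fall outside collection, so that the safety comparison is one-sided by construction. The documents do not support that, because the wider passages still apply and the blind largely prevents selective collection. A reader might also infer that every uncollected pregnancy is a missed SAE. Only abnormal outcomes are SAEs. Appendix 5 Section 5 treats an elective abortion without toxicity as an outcome to be noted on the pregnancy form, without expedited reporting.

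The reply does not remove the conflict. Section 8.3.5 hands the process to Appendix 5, so the wider text does not plainly override the narrow sentence. Protection by the blind also ends when the blind does. Partner SAEs can still reach the adverse event record, since Appendix 5 Sections 5 and 6 send abortions that qualify as SAEs and congenital anomalies to the Adverse Event eCRF.

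**Conclusion.** The point holds as an inconsistency with low impact. Appendix 5 Section 4 contradicts its own next paragraph and four other places in the protocol on whether placebo partner pregnancies are collected, and its restriction cannot be applied by blinded staff. If it were applied, ascertainment of one class of SAE would differ by arm. Whether that would happen cannot be told from the documents.

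The text comparison needs no assumption beyond the protocol's own definition of study treatment. The size rests on the planned numbers in Section 9.2 and on the assumed rate of 0.1% to 1% per year: 12 to 17 placebo participants and far fewer than one expected event. The reason to act is that an unworkable instruction, and a possible reason to unblind, can be removed at almost no cost.

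**What to change.** Replace the restricting sentence in Appendix 5 Section 4 with: *This applies to all male participants who receive study treatment (RO7239958 or placebo).* Appendix 5 then agrees with Sections 8.3.3.1 and 8.3.5 and Appendix 2 Section 5, and the site can follow it without knowing the assignment. No procedure is added beyond what those sections already require. The cost is one sentence and at most a few extra pregnancy follow-up forms.
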